4.10 Secondary Data – Records/Chart Reviews/Databases/Tissue Banks/etc. N/A

4.11 Chart/Record Review Selection

Version Number: 15, 2/2/2022 Protocol Number: Pro20190016877

PI Name: [name]

Protocol Title: Mindfulness Oriented Recovery Enhancement (MORE) as an Adjunct to Methadone Treatment RESERVED FOR IRB STAMP
DO NOT MODIFY THIS SPACE

4.12 Secondary Specimen Collection

N/A

5.0 Special Considerations

5.1 Health Insurance Portability and Accountability Act (HIPAA)

We will be obtaining individually identifiable health Information associated with a HIPAA-covered component or entity in the course of the research.

5.2 Family Educational Rights and Privacy Act (FERPA)

N/A

5.3 NJ Access to Medical Research Act

N/A

5.4 Code of Federal Regulations Title 45 Part 46 (Vulnerable Populations)

- A. "Special" Classes Of Subjects
 - (1) Pregnant Women: see guidance (HRP-412)
 - (2) Neonates: see guidance (HRP-413)
 - (3) Neonates of Uncertain Viability: see guidance (HRP-414)
 - (4) Prisoners: see guidance (HRP-415)
 - **(5)** Children: see guidance (HRP-416)
 - (6) Cognitively Impaired Adults: see guidance (HRP-417)

N/A

6.0 Research Data Protection and Reporting

6.1 Data Management and Confidentiality

A. Describe the data analysis plan, including any statistical procedures.

Data Analyses. Analyses will be conducted on an intent-to-treat basis. Adjustment for multiple comparisons using Bonferroni-Holm procedure²⁸ will be applied in outcome analyses. We will first examine baseline between-group differences on demographic and other key variables - those that show a difference of p<.10 will be entered as covariates in the analyses below. Given that this RCT occurs within a naturalistic treatment context (i.e. MMT programs in which study participants will also be receiving usual care), significant group differences in usual treatment (e.g., methadone dose or number of TAU psychotherapy sessions) will be treated as covariates. For all analyses specified below, we will perform sensitivity analyses to test response differences or clustering by site, group cohort, and therapist either as fixed or random effects and assess the robustness of results when accounting for these site and therapist effects. To handle **missing data**, we will conduct a series of sensitivity analyses using pattern-mixture (PM) approaches, ²⁹⁻³¹ assuming missing-at-random (MAR), ³² not-missing-at-random (nMAR) and/or a mix of nMAR and MAR, to assess plausible treatment effects in the presence of missing data. Other PM approaches such as control-based pattern imputation approach or the tipping-point approach will also be considered. ³³ The missing data handling strategy will be carefully selected depending on the distributions, type, and mechanism of missing data (informative vs. non-informative).

Version Number: 15, 2/2/2022 Protocol Number: Pro20190016877 PI Name: [name]

Protocol Title: Mindfulness Oriented Recovery Enhancement (MORE) as an Adjunct to Methadone Treatment RESERVED FOR IRB STAMP
DO NOT MODIFY THIS SPACE

AIM 1 Analyses.

Hypothesis 1.1. (**Primary Outcome**) MORE will result in longer duration of time to first opioid lapse and MMT dropout than TAU. We will use survival analysis (Kaplan Meier curves and marginal model analysis for multivariate survival data)³⁴ to test effects of MORE vs. TAU on time until first opioid lapse and MMT dropout—evidenced either on EMA, Timeline Follow-Back, urinalysis or medical records (whichever is first). Survival analysis will be run once, at 16 weeks post-baseline. Clustering within cohort will be adjusted in the multivariate marginal model analysis.³⁴ We will estimate the hazard ratios of opioid lapse and MMT dropout when comparing MORE with TAU, controlling for covariates.

Hypotheses 1.2 and 1.3 (Secondary Outcomes). MORE will result in more days of opioid abstinence (or less days of use) and a higher rate of biochemically-verified abstinence over time than TAU. Generalized linear mixed model (GLMM)³⁵ repeated measures analysis will be used. Specifically, identity link will be used for "number of abstinent days" as the dependent variable, and logit link will be used for "opioid abstinence (yes/no via urinalysis)" as the dependent variable. Days of use/abstinence will be assessed via EMA, number of drug use days since last visit and past 30 days, and the Timeline Follow-Back. In cases of conflicting findings across data sources, we will assume the highest number of days of use or lowest number of abstinent days recorded for that period. Analyses will include group (MORE vs. TAU), time, and group by time interactions as the fixed effects independent variables. Correlations among repeated measures and among subjects within cohorts will be modeled using nested random effects. Potential confounders that meet the p<0.10 criterion stated above will be entered as covariates. Linear contrasts will be constructed to test between-group differences in "days of use" or "days of abstinence" separately at each timepoint. In comparing days of use, if a substantial proportion of subjects do not use opioids, resulting in excessive zero days of use, we will use a two-part logistic/linear analysis model.^{36,37}

Hypotheses 1.4 (**Secondary Outcomes**). MORE will result in more days of MMT and greater decreases in pain severity, pain interference, days of non-opioid drug use, and emotional distress over time than TAU. We will use GLMM to compare days of MMT, pain severity and interference scores, days of non-opioid drug use, and emotional distress among the treatment groups, using the same analytic strategy described above.³⁵

AIM 2 Analyses. Mediational analysis. To test whether the three mediators specified in Aim 2 statistically mediate the effect of treatment on changes in days of opioid use over time, we will conduct a multivariate path analysis via a latent growth curve framework conducted in structural equation modeling software (i.e., MPlus) according to established guidelines³⁸ evaluating 3 regression paths for each mediator: A) 'a' path between treatment indicator and pre-post treatment change in the mediator (e.g., savoring); B) the 'b' path between pre-post treatment change in the mediator (e.g., savoring) and the latent slope (change) of the outcome (e.g., opioid use); and C) the 'c' path between treatment indicator and the latent slope of the outcome (e.g., opioid use). We will emulate similar multivariate analyses from published studies of meditation interventions^{39,40} by testing treatment effects on the latent slope of changes in days of drug use over time as mediated by changes in proposed mechanisms. We will test mediation by evaluating the significance of the joint product of the a and b paths, with bootstrapping used to test the significance of the indirect effect. A similar model will be estimated for changes in pain severity. Path models will be corrected for multiple comparisons. Simultaneous estimation of mediational effects from all three mediators to days of drug use and pain will allow us to determine unique effects of the core therapeutic mechanisms of MORE (mindfulness, reappraisal, savoring) – representing one of the most comprehensive mediation modeling attempts of the MORE intervention research program to date.

Version Number: 15, 2/2/2022 Protocol Number: Pro20190016877 PI Name: [name]

Protocol Title: Mindfulness Oriented Recovery Enhancement (MORE) as an Adjunct to Methadone Treatment RESERVED FOR IRB STAMP
DO NOT MODIFY THIS SPACE

Exploratory, temporally-dynamic analysis of the effects of mindfulness practice on EMA measures of craving, affect, and pain. Growth curve analyses and multivariate autoregressive latent trajectory analyses (m-ALT) of EMA data will examine antecedents and consequences of drug use as well as the impact of skill practice on craving and drug use. EMA data will yield granular analyses of process variables (mindfulness, reappraisal, and savoring practice) and quantify how skill use dynamically co-varies with pain, craving, and drug use during and after treatment. Lagged growth curve analyses⁴¹ will examine treatment and practice effects on: A) trajectories of positive/negative affect, craving, and pain; B) relationships among these variables over time; and C) how trajectories in affect, craving, and pain predict drug use in separate m-ALT models. The models, like ones published by [name], will estimate cross-lagged and autoregressive effects, as well as latent intercept and growth factors, among EMA variables, conditioned on a treatment group variable and measures of mindfulness, reappraisal, and savoring practice. EMA models will be corrected for multiple comparisons.

AIM 3 Analyses. To test gender as a moderator of treatment response, we will include all main effects and all two-way, and three-way interactions of gender, treatment, and time in GLMM analysis models, and all main effects and the two-way interaction of gender and treatment in the marginal multivariate survival analysis models. A significant gender x treatment x time interaction in GLMM models, tested by F test, indicates that treatment effect on changes in outcomes over time differ by gender. A significant gender x treatment interaction in survival models, tested by Wald test, indicates that treatment effect on time to event differs by gender. In GLMM analysis, gender differences on outcomes at 8, 16, 24, and 52 weeks will be estimated and tested using linear contrasts. Other potential moderators (e.g., race, income, mental health, trauma, and MMT phase) will be explored using similar approaches as exploratory analyses.

C11. Outcomes and Future Directions. We expect to establish the efficacy of an innovative intervention that can enhance MAT by supporting chronic pain management and MMT adherence while preventing drug use and opioid relapse. Results from this study will inform the development of services in New Jersey and other states seeking efficacious strategies to combat the opioid epidemic. If this study demonstrates MORE's efficacy as an adjunct to MMT, we will follow this study with a Stage IV implementation/dissemination study to enhance the rapidity and fidelity of uptake of the intervention into standard of care for persons with OUD.

B. Provide a power analysis. (As applicable, e.g. quantitative research)

We powered the R33 study based on data from prior research. We used a study of an MBI for substance users,⁴ which showed that the hazard ratio of relapse to drug use for the intervention compared to TAU was 0.46. We thus assumed a similar, but more conservative hazard ratio of relapse to opioid use of MORE compared to TAU at about 0.55. (We are using a slightly more conservative hazard ratio than in the original application due to the increased power obtained by reducing the number of treatment conditions from three to two.) We also assumed that the median relapse time to opioid use is 99 days, based on a prior study of relapse to drug use in a general MMT population.⁵ With 1.5 years of subject accrual and an additional follow-up of 16 weeks after the accrual interval, our study needs 47 subjects per group to test a hazard ratio of 0.55 when comparing MORE to TAU, with 80% power and alpha=5% (two-sided). To account for attrition, we will recruit 85 subjects per group (a total of 184 subjects at a 1:1 ratio for MORE vs. TAU).

Version Number: 15, 2/2/2022 Protocol Number: Pro20190016877

PI Name: [name]
Protocol Title: Mindfulness Oriented
Recovery Enhancement (MORE) as an
Adjunct to Methadone Treatment

RESERVED FOR IRB STAMP DO NOT MODIFY THIS SPACE

C. Describe the steps that will be taken secure the data (e.g., training, authorization of access, password protection, encryption, physical controls, certificates of confidentiality, and separation of identifiers and data) during storage, use, and transmission.

All investigators and research staff will have undergone mandatory education in human research participant protection. To assure confidentiality, data will be secured in a database management system, password protected files, and in secure file cabinets. Data collection forms, databases, and recordings will not include identifiers other than a study ID code. The key to the code will be kept separately in a locked and/or password protected file for no longer than six years. Informed consent forms will be kept separately in a locked file in the same office. Three levels of security are provided to prevent unauthorized persons from accessing the data: password protection, computer or file cabinet locks, and a locked office. In addition, we have a Certificate of Confidentiality from the National Institutes of Health that protects study data from subpoena. Access to data will be limited study investigators and staff. Research data will be kept no longer than 10 years.

D. Describe any procedures that will be used for quality control of collected data.

As we have done in prior studies, protocols will be developed during the initial start-up period that explicitly describes the specific procedures related to data collection, entry, storage, and quality assurance for both study conditions. Data will be collected by research staff in strict accordance with the study's protocols. All data collected will be independently reviewed for quality and consistency by a member of the research team who was not responsible for collecting the source data. The research staff will be trained to avoid omissions in data collection and data entry. Computer entry protocols will be programmed to avoid accidental skipping of question items. We will apply conditional formatting to datasheets to remove the possibility of out of range data. Data will be entered directly into a secure Qualtircs or REDCap databases. Under supervision from [name], the Research Assistant will conduct monthly descriptive summaries on all data to ensure their accuracy. This will not involve completing any statistical comparisons. If problems are noted in data entry (e.g., out of range values, missing values), the Research Assistant and [name] will investigate the root cause, and solutions to rectify the problem will be generated and implemented.

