8	Discussion of how to maintain mindfulness practice; finding a sense of meaning and purpose of life; development of mindful recovery plan; imaginal rehearsal of skill learning; mindful breathing							

Treatment as Usual (TAU). In the MMT programs, clients typically come to the clinic regularly (usually 6 days per week at the beginning of treatment) to get their methadone dose; during periods of social distancing or as clients progress through the program and remain abstinent from drugs, they can "take home doses" that they can take on days that they are not required to come to the clinic. Timing of the initiation of take-home doses and the scheduling of clinic days varies across clinics. Clients see their clinic substance abuse counselor for individual

7

Version Number: 15, 2/2/2022 Protocol Number: Pro20190016877 PI Name: [name]

Protocol Title: Mindfulness Oriented Recovery Enhancement (MORE) as an Adjunct to Methadone Treatment RESERVED FOR IRB STAMP
DO NOT MODIFY THIS SPACE

counseling, usually weekly at the beginning of treatment, with decreasing frequency if they remain abstinent and progress through treatment. Depending on clients' stage of MMT and success with remaining abstinent from drugs, they may be required to attend clinic treatment groups. During periods of social distancing, these individual or group sessions may be remote, through video conference or phone. Also, some clients may choose to go to voluntary counseling, educational, or support groups (none of these groups involve coping with pain oriented or are mindfulness-based). All individual treatment characteristics, including methadone dosage, take-home dosing, clinic attendance and attendance at clinic counseling sessions and groups (whether in-person or remotely), will be documented for all study participants and entered as covariates in the analyses.

B. Dependent Variables or Outcome Measures

In addition, the study will explore outcomes among participants in the MORE condition relative to treatment as usual (TAU) in regard to opioid use outcomes such as:

- Time until first opioid lapse (primary outcome)
- Opioid abstinence
- Time until MMT dropout
- Total days of methadone treatment
- Total days of opioid or any drug use
- Trajectories of positive and negative affect
- Drug craving
- Pain severity and pain interference

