An initial eligibility screen will be conducted over the phone. Based on the initial screening, if further screening measures are needed, they will be done after the patient consent.

Inclusion Criteria

Only individuals meeting all of the inclusion criteria at baseline will be able to participate in the study. Subjects must be age 18 or older, English-speaking, currently on methadone, and have been experiencing non-malignant pain with an intensity level of 8 or higher on the Gracely Box Scale¹³ or pain ≥3 out of 10 on the BPI average pain severity item for 3 months or longer.

Exclusion Criteria

Subjects will be excluded from participation if they do not meet the inclusion criteria above exhibit cognitive impairment (based on observation, history, clinician feedback, or score <24 on the Mini Mental Status Exam¹⁹) or psychosis (based on observation, history, clinician feedback, or positive SCID Psychotic Screen²⁰), are at suicidal risk (based on observation, history, clinician feedback, or positive score on C-SSRS), unable to attend group sessions for any reason, or participated in formal mindfulness training within the past 5 years.

E. Recruitment Materials

Flyers with study information and a phone number to reach research staff will be posted throughout the New Brunswick Counseling Center (NBCC), Burlington Comprehensive Counseling, JSAS, and the Lennard Clinic.

17

F. Lead Site Recruitment Methods

N/A

Version Number: 15, 2/2/2022 Protocol Number: Pro20190016877

PI Name: [name]

Protocol Title: Mindfulness Oriented Recovery Enhancement (MORE) as an Adjunct to Methadone Treatment RESERVED FOR IRB STAMP
DO NOT MODIFY THIS SPACE

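### The two rules for usual-treatment covariates conflict and neither excludes values measured after randomization; separately, baseline covariates are chosen by a p<.10 imbalance test over an unlisted set

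*Combined protocol and SAP*

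**What the plan says.** **Usual-treatment variables.** Section 1.6 A, in the description of treatment as usual, names methadone dosage, take-home dosing, clinic attendance, and attendance at counseling sessions and groups. It says these "will be documented for all study participants and entered as covariates in the analyses". No condition is attached. Section 6.1 A has a different rule: "significant group differences in usual treatment (e.g., methadone dose or number of TAU psychotherapy sessions) will be treated as covariates". It gives no significance level and no measurement window.

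**Baseline variables.** Section 6.1 A compares the arms at baseline on "demographic and other key variables", and "those that show a difference of p<.10 will be entered as covariates in the analyses below". No list of variables follows. For the secondary mixed models the rule is repeated: "Potential confounders that meet the p<0.10 criterion stated above will be entered as covariates".

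**Where the covariates go.** They enter the primary analysis. Under Hypothesis 1.1: "We will estimate the hazard ratios of opioid lapse and MMT dropout when comparing MORE with TAU, controlling for covariates". Kaplan-Meier curves are planned, but no unadjusted primary test or estimate is named. The sensitivity analyses in section 6.1 A deal with site, cohort, therapist and missing data, not with the choice of covariates.

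**The concern.** Two analysts who follow sections 1.6 and 6.1 faithfully can fit different primary models, and no text says which section governs.

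The more serious matter is timing. Attendance and session counts build up during the trial. Section 1.6 A makes take-home doses available "as clients progress through the program and remain abstinent from drugs", and says that counseling becomes less frequent for clients who stay abstinent. Section 1.1 B hypothesizes that MORE improves adherence to methadone treatment. These variables may therefore be consequences of the randomized treatment, of the outcome, or of both. Hypothesis 1.1 also includes methadone dropout, which overlaps with attendance. Conditioning on such variables breaks the comparison that randomization protects.

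The p<.10 screen is a lesser fault. Under randomization it selects on chance imbalance rather than on prognosis, and the primary model is known only after arms have been compared. The entry criteria ("Subjects must be age 18 or older, English-speaking, currently on methadone, and have been experiencing non-malignant pain") do not require abstinence, so opioid use at entry may vary and is likely to predict lapse. The screen would still usually leave it out.

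**Working it through.** No sample size, power or alpha figure in the plan depends on this point, so there is none to reproduce. The check sets the rules side by side and then illustrates what follows.

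**1. The two rules**

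| | Section 1.6 A | Section 6.1 A |
|---|---|---|
| Entry | always | only if the arms differ significantly |
| Level | not applicable | not stated |
| Time window | none | none |
| Precedence over the other | not stated | not stated |

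**2. Adjusting for attendance**

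Inputs from the documents: 92 per arm (section 1.5); 16 weeks, or 16 × 7 = 112 days; hazard ratio 0.55 and median 99 days (section 6.1 B). The arm to which the 99 days applies is not stated; it is taken here as TAU, so λ = ln 2 / 99 per day.

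Assumptions not in the documents: an unmeasured adherence factor U ~ N(0,1); attendance M = g·(MORE) + 0.7U + 0.7e, with e ~ N(0,1); hazard = λ·exp(ln HR·(MORE) − 0.5U). The shift g is 0, 0.3 or 0.5. Lapse is analyzed alone by Cox regression, without clustering or attrition. There were 500 trials per scenario.

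M always entered, as in section 1.6:

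| g | Adjusted HR, true 1.0 | Rejection, true 1.0 | Adjusted HR, true 0.55 | Power, true 0.55 |
|---|---|---|---|---|
| 0 | 1.01 | 5% | 0.56 | 76% |
| 0.3 | 1.11 | 7% | 0.62 | 57% |
| 0.5 | 1.19 | 13% | 0.68 | 40% |

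Without adjustment, rejection under the null is about 5% and power is 69 to 75%. If M is entered only when the arms differ at p<.05 (one reading of section 6.1), null rejection is about 6% and 13% for g = 0.3 and 0.5.

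Further runs of this kind of model gave null rejection of 11 to 20% under section 1.6 and 9 to 18% under section 6.1. Power fell from about 67% to 48 to 29% and to 53 to 30% respectively. Raising the coefficient on U from 0.5 to 0.7 is enough to reach these values, with an adjusted hazard ratio up to about 0.72. The conditional rule gives little protection, because a shift caused by treatment is what triggers entry. The excess rejections under the null are hazard ratios above 1.

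**3. Adjusting for take-home status**

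Assumptions: 30% using at entry with prognostic hazard ratio 2; probability of take-home status 0.6 to 0.7 if lapse-free and 0.1 to 0.4 if lapsed; unadjusted mean hazard ratio 0.56.

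| Rule | Measured | Adjusted HR | Power lost |
|---|---|---|---|
| Always entered | week 8 | 0.56–0.57 | 1–5 points |
| Always entered | week 16 | 0.57–0.61 | 2–15 points |
| Entered if p<.05 (6–25% of trials) | either | 0.56–0.59 | 0–9 points |

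Null rejection here stays at 3.8 to 5.9%. The damage is milder when the variable depends on lapse alone.

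**4. The p<.10 screen**

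Any one variable enters by chance with probability 0.10, so it is left out about 90% of the time. With k independent candidates, P(at least one enters) = 1 − 0.9^k. For k = 10 this is 1 − 0.349 = 65%; for k = 20 it is 1 − 0.122 = 88%.

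For the power cost, assume 20 to 40% using at entry, hazard ratio 0.55 in users and non-users, 92 per arm and 112 days. Compare the rule with pre-specified stratification on baseline use:

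| Prognostic HR of baseline use | Rule | Stratified | Loss |
|---|---|---|---|
| 1.5 | – | – | about 0–2 points |
| 2 | 74–75% | 76–77% | about 2 points |
| 3 | 70–71% | 75–77% | about 4–6 points |

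Type I error under the screen was 3.1 to 4.9%.

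**The case against.** **Section 6.1 is the analysis section and would prevail.** An analyst would probably follow it over a remark in the description of TAU. That softens the conflict but does not remove the main problem: section 6.1 has no time limit either, and its own example, the number of psychotherapy sessions, accrues during care.

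**Usual treatment may mean baseline values.** The text does not exclude this. The point is therefore that the rules can admit post-randomization values, not that they must. A reader might infer that the team has committed to adjusting for them; section 6.1 does not go that far.

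**The sizes rest on assumptions.** This stands. The shift in attendance, the shared factor, the share of users and the prognostic hazard ratios appear nowhere in the plan. The planned model is a marginal model for two events with cohort clustering, not the single-event model used here.

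Four stronger readings are tempting and are not supported:

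- *The p<.10 screen inflates type I error.* It does not. The inflation arises only with post-randomization covariates.
- *The inflation means false claims of benefit.* In the illustrations the excess rejections favor TAU. The documents do not fix the direction for every variable: section 1.6 says counseling becomes less frequent with abstinence, the opposite sign to the attendance model.
- *The screen biases the hazard ratio toward 1.* At prognostic hazard ratio 3 the mean is 0.57 under the screen and 0.55 stratified. This is non-collapsibility: the two models estimate different quantities.
- *Treatment phase is left out of the screen.* The set of other key variables is undefined, so it may be included.

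**Conclusion.** The point holds and should be corrected. The conflict between sections 1.6 and 6.1, and the absence of any limit to pre-randomization values, are plain on the text.

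The potential harm to the primary hazard ratio ranges from small, when a variable merely reflects lapse, to large, when MORE shifts attendance and attendance shares causes with lapse. In the latter case, under the stated assumptions, null rejection is about 7 to 20%, and a true 0.55 is estimated at about 0.62 to 0.72 with power of about 30 to 57%. These figures show plausible size and are not forecasts.

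The baseline screen is a separate and lesser defect. It leaves the primary model unfixed and costs little power unless a strong predictor is left out.

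**What to change.** 1. Replace the rules in sections 1.6 A and 6.1 A with one rule: covariates in the primary and secondary efficacy models are limited to values measured before randomization. Usual-treatment variables measured later are reported descriptively or used in labeled sensitivity analyses only.
2. Delete the p<.10 screen in both places in section 6.1 A. Put one fixed, named list of baseline covariates in its place, used whatever the observed imbalance.
3. The natural candidate for that list is baseline non-prescribed opioid use, already collected under section 1.9 B. Its definition should not count methadone or a prescribed opioid as positive, since the drug screen includes methadone and some participants are prescribed opioids for pain.
4. Lock the list before anyone sees outcomes by arm, including at the interim analysis that section 6.3 E allows at 50% accrual.

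The cost is wording and slightly more modelling; no new data are needed. Stratifying on baseline use could cost up to about 4 points of power if MORE has no effect in people using at entry. That is a reason to settle the list deliberately, not to keep the screen.

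### The two usual-care covariate rules conflict and neither is limited to baseline, so care received after randomization can enter the primary hazard-ratio model

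*Combined protocol and SAP*

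**What the plan says.** Section 6.1 A sets the principle: "Analyses will be conducted on an intent-to-treat basis". It then gives a baseline rule: "We will first examine baseline between-group differences on demographic and other key variables", and "those that show a difference of p<.10 will be entered as covariates in the analyses below".

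The next sentence is a separate rule for usual care. Its reason is that "study participants will also be receiving usual care", and it says that "significant group differences in usual treatment (e.g., methadone dose or number of TAU psychotherapy sessions) will be treated as covariates". It states no significance level and no time point.

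Section 1.6, under Treatment as Usual, has a different rule. "All individual treatment characteristics, including methadone dosage, take-home dosing, clinic attendance and attendance at clinic counseling sessions and groups" "will be documented for all study participants and entered as covariates in the analyses". This one does not depend on a group difference, and it also gives no time point.

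Under Hypothesis 1.1 in Section 6.1 A, the hazard ratios for opioid lapse and for MMT dropout are adjusted for covariates that are not named. For the secondary mixed models, Hypotheses 1.2 and 1.3 repeat only the p<0.10 screen, and Hypothesis 1.4 reuses that strategy. Section 1.9 B takes methadone dose, treatment days and services from clinic charts, again with no time window.

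**The concern.** There are two defects. First, the two usual-care rules give different covariate sets whenever a usual-care variable does not differ significantly between arms, so the primary model is not determined in advance.

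Second, nothing confines usual care to its value at or before randomization. Later values can be consequences of lapse, consequences of MORE, or both. Conditioning on them changes what the hazard ratio estimates. A real effect can be partly adjusted away. If MORE itself changes usual care, a null effect can look like benefit or harm.

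No planned analysis would reveal this. The sensitivity analyses cover site, cohort, therapist and missing data, and no unadjusted test is named alongside the Kaplan-Meier curves.

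**Working it through.** **1. The rules side by side**

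| | Section 1.6 | Section 6.1 A |
|---|---|---|
| Enters the model | every usual-treatment characteristic | only those differing significantly |
| Threshold | none needed | needed, not given |
| Measurement time | not given | not given |

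**2. Is the Section 6.1 rule a baseline rule?** The word baseline stands in the preceding sentence, which has its own p<.10 criterion. The usual-care sentence has a different criterion, a rationale that looks to care during the study, and a session count as an example. The natural reading includes care after randomization. Methadone dose could be a baseline value.

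**3. Do the rules reach the primary model?** Before Hypothesis 1.1 the analysis plan gives only the baseline screen and the usual-care sentence. The covariates mentioned there can only come from these general rules. Reach into the secondary mixed models is less clear.

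**4. Are the variables linked to the outcome?** Section 1.6 says of take-home doses that "during periods of social distancing or as clients progress through the program and remain abstinent from drugs, they can" take them. Counseling becomes less frequent with abstinence, and required groups depend on it. Clinic attendance overlaps MMT dropout, which Section 1.9 B dates to the last methadone dose. Two points limit this. Section 1.6 also names social distancing and the clinic as drivers of take-home timing. Sections 1.1 B and 4.2 D allow entry in the maintenance phase, when status may already be settled. The documents show no such link for methadone dose.

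**5. Illustrative size**

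Inputs from the documents: 92 per arm (Section 1.5), 16 weeks = 112 days (Section 1.3 C), hazard ratio 0.55, two-sided 5% and a median of 99 days, taken as the TAU median (Section 6.1 B).

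Unadjusted reference, exponential times:
- TAU event probability: 1 − exp(−112·ln2/99) = 0.543
- MORE event probability: 1 − exp(−0.55·112·ln2/99) = 0.350
- Expected events: 92 × (0.5435 + 0.3503) = 82.2
- Power: Φ(√(82.2/4)·0.598 − 1.96) = Φ(0.75) ≈ 77%

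Simulated unadjusted Cox models agree: hazard ratio 0.54-0.55, power 74%-79%.

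All association strengths below are assumed. Unless stated otherwise, each scenario has 2,000 replicates, no clustering, and usual care entered as one fixed value per person.

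*Take-home status.* The probability of take-home status is 0.6/0.7/0.8 without lapse and 0.3/0.2/0.1 with lapse. "Fixed" participants have a status unrelated to lapse. Always adjusted, as in Section 1.6:

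| Fixed at entry | Hazard ratio | Power |
|---|---|---|
| none | 0.56/0.60/0.66 | 72%/61%/44% |
| 25% | 0.55/0.58/0.61 | 75%/67%/60% |
| 50% | 0.55/0.55/0.57 | 76%/75%/69% |
| 75% | 0.55 throughout | 74%-76% |

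Under the Section 6.1 rule, with p<.05 assumed and none fixed, the covariate enters in 11%/25%/41% of trials. The hazard ratio is then 0.55/0.58/0.63 and power 75%/68%/54%. With half or more fixed it is 0.55-0.56, with power 73%-77%.

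*Session counts.* Always adjusted: hazard ratio 0.55-0.71, power 77%-32%; mild patterns leave 0.55-0.56. Under the Section 6.1 rule: 0.55-0.67. A separate simulation (1,000 replicates) counted weekly sessions only until lapse or week 16. The hazard ratio moved from 0.56 to 0.76, power from 74% to 25%, and type I error from 5.3% to 10.9%.

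*No true effect.* The covariate shares a prognostic cause with lapse, and MORE shifts it. Rejection rates when always adjusted:
- No shift: about 5%-6%.
- Shift 0.1-0.25 SD: 4.7%-10.5% (Section 6.1 rule: 4.2%-7.0%).
- Shift 0.5-1 SD, correlation 0.3: 6%-19%.
- Shift 0.5-1 SD, correlation 0.6: 10%-61%.

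Shift and correlation of the same sign give apparent benefit; opposite signs give apparent harm.

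*MMT dropout.* A hazard ratio of 0.55 and 50% TAU dropout at 12 months are assumed; the latter figure in Section 1.2 concerns people starting MMT. Participants are assumed to attend 90% of scheduled days. Unadjusted: 0.53-0.54. Adjusted for attendance counts: 0.54-0.56 if schedules span 1-6 days a week, 0.69 if they span 3-6.

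**The case against.** The wording permits post-randomization values but does not require them. The usual-care sentence follows one about baseline, so a baseline reading is available, though it is weak for a session count. This stands as a limit: the bias is conditional, while the conflict and the missing time point are certain.

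The stronger objection concerns coding. Everyone still at risk of a first lapse is lapse-free on study, so dilution by lapse-driven care needs a covariate that carries post-lapse information. In a check with take-home status time-updated before lapse, the hazard ratio was 0.53 with 80% power (400 replicates). A fixed covariate reflecting only pre-lapse status gave 0.55, with power unchanged at 75%-77%. That is correct, but the plan does not provide for time-updated coding. Section 6.1 compares one value per person between groups, so a fixed value is the natural reading. Nor does time-updating remove the route in which MORE changes usual care, although the documents give no evidence that it does.

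The larger figures mostly come from always adjusting. The Section 6.1 screen softens them, and it was not run for the 0.5-1 SD shifts. The 61% needs a large shift and a correlation of 0.6.

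**Conclusion.** The concern holds and needs correcting before analysis. From the text alone, the usual-care covariate set for the primary model is contradictory, has no threshold and is open to post-randomization values. Section 1.6 links several of those variables to abstinence, so adjusting for later values would defeat the intent-to-treat aim.

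The size is not established. It ranges from no visible effect to a hazard ratio of 0.66-0.76 in place of about 0.55, with power falling to 25%-44%. These figures rest on assumed associations, on fixed per-person coding that carries information on the lapse or its timing, and on the share of participants whose usual care is already settled at entry. Type I error is at risk mainly if MORE shifts usual care or if sessions are counted only up to lapse. Confidence is high for the defect in the rules, not for any single figure.

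**What to change.** Reconcile Sections 1.6 and 6.1 A into one covariate rule and refer to it by name under Hypothesis 1.1 and in the secondary mixed models. Adjust only for a prespecified list of variables measured at or before randomization, for example baseline methadone dose, baseline take-home status and time in MMT. The time restriction is what removes the bias. The fixed list also replaces selection by significance, including the p<.10 baseline screen, which goes somewhat further than the bias alone requires but settles the model in advance.

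Report usual care after randomization descriptively by arm. Keep any adjustment for it as a labeled supportive or mediation analysis. If baseline values were always intended, a clarifying sentence in each section and a choice between the two rules would do. The cost is protocol and SAP wording; data collection is unchanged.
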